11.4.2.2 Analysis of secondary efficacy endpoint(s)

Nocturnal symptomatic hypoglycemia will be defined as an event with typical symptoms of hypoglycemia accompanied by SMPG \leq 70 mg/dL (3.9 mmol/L) that occurs between 00:00 and

05:59 hours. The incidence will be analyzed using logistic regression, adjusting for randomization strata and other baseline characteristics (duration of diabetes, BMI and age) as clinically appropriate and if the model permits.

The rate per patient-year of nocturnal symptomatic hypoglycemic events will be analyzed using an over-dispersed Poisson regression model, adjusting for randomization strata and other baseline characteristics (duration of diabetes, BMI and age) as clinically appropriate and if the model permits.

The percentage of time glucose concentrations obtained by CGM within the target range of 70-140 mg/dL (3.9-7.8 mmol/L) during the last 4 hours of CGM data prior to the next day basal insulin injection will be calculated as the total time within that time period that the plasma glucose is in the range, divided by the length of that time period of observation.

The period of observation for the calculation will comprise of the last 4 hours during the final evaluable 24-hour period, where the evaluable period is defined as for the primary endpoint.

Total, within day and between day coefficient of variation (calculated for each period as the ratio of the standard deviation of the glucose values to mean of the glucose values).

Both the percentage of time glucose concentrations within the target range of 70-140 mg/dL (3.9-7.8 mmol/L) and the total, within day and between day coefficient of variation will be summarized at baseline and study endpoint by treatment group using mean, median, standard deviation, minimum and maximum, and will be analyzed as for the primary endpoint.

Other endpoints

The frequency and rates (nocturnal or 24 hours) of all hypoglycemic events will be analyzed for the hypoglycemia categories of severe, documented symptomatic, asymptomatic, probable and relative, as defined in the publication of the ADA Workgroup on Hypoglycemia, 2015. These hypoglycemia categories will be analyzed as for symptomatic hypoglycemia described previously.

The percentage of time plasma glucose in target range 70-140 mg/dL (3.9–7.8 mmol/L), and the percentage of time plasma glucose \leq 70 mg/dL (3.9 mmol/L) and \leq 54 mg/dL (3 mmol/L) will be calculated and analyzed as for the primary endpoint. For these endpoints, the time period of observation will be all evaluable time (24hours) and nocturnal, where nocturnal is defined as the period between 00:00-05:59 within the evaluable assessment interval.

The area under the curve (AUC) of glucose concentration ≤70 mg/dL (3.9 mmol/L) will be derived as the area above the CGM profile (ie, the median curve) and below this lower limit of the glycemia range, divided by the length of the evaluable assessment interval. The median curve will be obtained by superimposing the date-time-stamped glucose values collected by CGM into 24 nominal hourly baskets from which the point-wise median is calculated.

The AUC of glucose concentrations >180 mg/dL (10 mmol/L) will be derived as the area below the CGM profile (ie, the median curve) and above the upper limit of the glycemia range, divided by the length of the assessment interval. The median curve will be derived as defined previously.

All of the continuous CGM endpoints will be summarized, and will be analyzed using a generalized linear model as described for the primary endpoint.

The absolute values and change in 7-point SMPG profiles (pre-prandial and 2-hour post-prandial plasma glucose at breakfast, lunch and dinner, and bedtime) from baseline to Week 12, Week 16 and the last on-treatment value (study endpoint) will be presented descriptively by treatment group.

Summary statistics will also be presented for the absolute values and the change from baseline in HbA1c and central lab FPG to Week 8, Week 16 and last on-treatment value (study endpoint). The change from baseline to study endpoint will be analyzed using a mixed-effect model with repeated measures (MMRM) approach under the missing at random framework, using an adequate contrast at endpoint. The model will include fixed categorical effects of treatment arm, visit, treatment-by-visit interaction, randomization strata, and baseline HbA1c as covariate as well as baseline HbA1c-by-visit interaction.

Insulin dose (total daily dose (units, units/kg), basal, mealtime/bolus, ratio of basal to bolus insulin dose) will be descriptively summarized for absolute values and change from baseline.

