11.4.2 Analyses of efficacy endpoints

11.4.2.1 Analysis of primary efficacy endpoint(s)

The percentage of time plasma glucose within target range of 70-180 mg/dL (3.9–10 mmol/L) during Weeks 15-16 (obtained from CGM) will be calculated based on the total time within glycemic range in the evaluable assessment interval, divided by the total time of the evaluable assessment interval.

The evaluable assessment interval for the calculation will comprise of 24-hour periods during Weeks 15-16 for which there is sufficient non-missing data. In order to be evaluable for analysis, a patient needs at least 4 days of 24-hour data meeting this criterion and should not receive protocol prohibited medication.

The endpoint will be summarized by treatment group using mean, median, standard deviation, minimum and maximum.

Differences between treatment groups will be explored using a generalized linear model, adjusting for key baseline characteristics (duration of diabetes, BMI, age and baseline value) and randomization strata. Adjusted mean estimates for each treatment with standard errors, the adjusted estimate of treatment mean difference with standard error and a 95 % confidence interval for the treatment mean difference will be provided. The statistical test will be for superiority of Toujeo over Lantus, two-sided and at a 5% significance level.

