2.1.3 Efficacy endpoints

The baseline value for efficacy parameters is defined as the last available value before the first injection of IMP.

Baseline CGM measurements will start at Visit 2 and stop at randomization visit (Visit 3).

Observation period for efficacy endpoints

- The on-treatment period for efficacy variables is defined as the time from the first dose of IMP up to:
 - Seven (7) days after the last dose of IMP for HbA1c,
 - One (1) day after the last dose of IMP for hypoglycemia,
 - One (1) day after the last dose of IMP for FPG, SMPG and CGM,
 - Zero (0) day after the last dose of IMP for insulin glargine dose.
- The randomized period for efficacy variables is defined from the first dose of IMP up to Week 16 (visit 19).

All efficacy parameters will be performed on on-treatment period and randomized period.

All CGM derived variables will be subject to the following criteria.

1. CGM data are blinded to both the patients and investigators.
2. During the CGM performing week, the IMP insulin (Toujeo or Lantus) dose is fixed without a change, while the mealtime insulin dose can still be adjusted appropriately.

3. A complete 24-hour CGM profile includes 288 data points given that CGM reading is recorded every 5 minutes.
4. The start and end time of a 24-hour CGM profile is defined as midnight. i.e. each CGM profile begins at midnight (hour 0) and ends at midnight (hour 24 = hour 0). Partial CGM data points prior to the first midnight and after the last midnight from the visit will not be used in the CGM parameter calculation as the partial CGM profile may introduce additional variabilities to the data.
5. Useable CGM data for a day/a 24-hour CGM profile are defined as at least 85% time of records (245 data points) without a gap (missing data) lasting for ≥ 2 hours per 24 hours. At least 4 days of qualified 24-hour CGM records for each patient will be used for efficacy analyses. If the partial CGM data described in previously have at least 85% of a full CGM profile or 245 data points, the partial CGM profile will be used to calculate CGM parameters.
6. In cases that there are more than 288 data points or more than one data point per 5 minutes, usually due to recalibration or switching CGM devices, it will be reviewed and treated case by case. Usually averaging the data points every 5 minutes will be performed so that there is only one data point per 5 minutes.

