2.4.4 Analyses of efficacy endpoints

2.4.4.1 Analysis of primary efficacy endpoint(s)

The percentage of time glucose in target range 70-180mg/dL (3.9–10mmol/l) during week 16 (obtained from CGM) will be calculated based from the denominator of total time with valid data. The criteria to evaluate baseline and Week 16 CGM data are in Section 2.1.3.

The evaluable assessment interval for the calculation will comprise of 24-hour periods during Week 16 for which there is sufficient non-missing data. In order to be evaluable for analysis, a patient needs at least 4 days of 24-hour data meeting this criterion and should not receive protocol prohibited medication.

The endpoint will be summarized by treatment group using mean, median, standard deviation, minimum and maximum.

Differences between treatment groups will be assessed using a generalized linear model with identity link, adjusting for key baseline characteristics (duration of diabetes, baseline BMI, age and baseline value) and randomization strata if model permits. If model does not converge, for example due to over 90% patients fall into the carbohydrate counting, the specific factors which cause non convergence may be dropped from the model. Adjusted mean estimates for each treatment group with standard errors, the adjusted estimate of treatment mean difference with standard error and a 95 % confidence interval for the treatment mean difference will be provided. The statistical test will be for superiority of Toujeo over Lantus, two-sided and at a 5% significance level.

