2.4.4.3 Multiplicity issues

Results of the secondary analyses are considered as informative only if the primary analysis is positive, and will be examined in a hierarchical step-down manner. The primary efficacy endpoint, the percentage of time glucose in target range 70-180mg/dL (3.9–10 mmol/l) during Week 16, will be tested first, followed by (1) incidence of nocturnal symptomatic hypoglycemia, (2) rate of nocturnal symptomatic hypoglycemia, (3) mean change of each participant's glucose level during the last four hours of CGM (4) percentage (%) of time glucose concentrations obtained by CGM within target range of 70-140 mg/dL (3.9–7.8 mmol/L) during the last 4 hours of CGM data collection prior to next day basal insulin injection, (5) total CV%, (6) within day CV% and (7) between day CV% . Each test was planned to be performed at 5% significance level. Inferential conclusions about these successive efficacy endpoints will require statistical significance of the previous one.

For other secondary and exploratory endpoints, nominal p-values will be presented for information only.

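### The only formula for pre-injection time in 70-140 mg/dL divides by the full 4 hours; the SAP does not restate the denominator as valid time, as it does for the primary endpoint

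*Protocol*

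**What the plan says.** SAP 2.4.4.3 tests the primary endpoint and then seven secondary endpoints in a fixed order. The fourth secondary is listed as "4) percentage (%) of time glucose concentrations obtained by CGM within target range of 70-140 mg/dL", taken over the 4 hours before the next basal injection. On the level, the section says: "Each test was planned to be performed at 5% significance level". Each step needs significance at the one before it, so the three coefficient-of-variation endpoints sit behind this one.

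The formula is in Protocol 11.4.2.2: "total time within that time period that the plasma glucose is in the range, divided by the length of that time period of observation". The next sentence fixes the period: "The period of observation for the calculation will comprise of the last 4 hours during the final evaluable 24-hour period".

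The SAP has no formula of its own for this endpoint. Section 2.1.3.2 names it, and section 2.4.4.2 gives only the model. For the other percent-time endpoints, including the nocturnal ones, section 2.4.4.2 goes further and carries over the primary endpoint's calculation as well. Section 2.5.3 covers missing injection times for this endpoint and sensor values beyond the detection limits, but not missing readings. The modifications in section 1.6 leave the denominator alone.

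For the primary endpoint, the Protocol synopsis and SAP 2.1.3.1 and 2.4.4.1 agree that the percentage "will be calculated based from the denominator of total time with valid data". Protocol 11.4.2.1 words it differently: "divided by the total time of the evaluable assessment interval".

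A usable day, under SAP 2.1.3 item 5, has "at least 85% time of records (245 data points) without a gap (missing data) lasting for ≥ 2 hours per 24 hours". No rule sets coverage for the 4-hour window itself.

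**The concern.** Glucose is known only while the sensor records. If the denominator is always 240 minutes, a missing reading adds to the denominator and can never add to the numerator. The value then depends partly on data capture in the hours before injection, for example whether the receiver stayed within its 20-foot range (Protocol 10.2.4.1), and not only on glucose.

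The sponsor avoided this for the primary endpoint by dividing by valid time, and extended that calculation to the other percent-time endpoints. This endpoint was left with the Protocol formula. Two programmers could therefore derive different values from the same data for an endpoint in the confirmatory sequence.

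**Working it through.** **Inputs from the documents**

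- One reading every 5 minutes, 288 per full day (SAP 2.1.3, item 3).
- A usable day has at least 245 readings and no gap of 2 hours or more (SAP 2.1.3, item 5; Protocol 10.2.4.2).
- The window is 4 hours (Protocol 11.4.2.2).
- At least 4 usable days are needed, and daily values are averaged (SAP 2.1.3, items 5 and 9).

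**Assumed, because the documents give no figures:** the true percentage in range in the window, its SD, and the capture rate.

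1. *The plan's own figure.* 0.85 × 288 = 244.8, rounded up to 245. This reproduces the SAP. A usable day may therefore lack 288 − 245 = 43 readings.

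2. *Window size.* 240 minutes / 5 = 48 readings.

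3. *Literal formula.* Let m of the 48 readings be missing and let p be the share of recorded readings in range. The calculated value is p × (48 − m)/48. The relative understatement is m/48, whatever p is.

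4. *One permitted gap.* Two hours is 24 readings, so the longest allowed run is 23. 23/48 = 47.9%. The day still qualifies, with 288 − 23 = 265 readings (92.0%). With p = 40%, the result is 40 × 25/48 = 20.8%, a loss of 19.2 points; dividing by valid readings gives 40%. If a gap is measured between the readings on either side of it, the longest run is 22, and 22/48 = 45.8%.

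5. *Patient level.* Take one such day averaged with complete days of similar value. Over 4 days, 47.9%/4 = 12.0%. Over 7 days, 47.9%/7 = 6.8%. Protocol 11.4.2.2 taken alone uses only the final usable day, which would not dilute the loss.

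6. *Average capture.* If capture in the window is unrelated to glucose, the understatement is one minus capture:

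| Assumed average capture | Relative understatement |
|---|---|
| 97% | 3% |
| 95% | 5% |
| 90% | 10% |
| 85% | 15% |

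7. *Effect on the test.* With constant capture, the difference and the SD shrink by the same factor and the test statistic does not change. Only variation in capture between patients costs power. Assume a mean of 40 and an SD of 20 points, with capture independent of glucose.
   - Capture 95% with SD 5 points: variance = (0.95 × 20)² + (40 × 0.05)² + (20 × 0.05)² = 361 + 4 + 1 = 366. The standardized effect kept is 19/√366 = 99.3%.
   - Capture 85% with SD 10 points: variance = 289 + 16 + 4 = 309. The standardized effect kept is 17/√309 = 96.7%.

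8. *Coverage in the window.* With several gaps, all 43 permitted missing readings could fall in the window: 43/48 = 89.6%. That leaves 5 readings (25 minutes) on a usable day. This coverage point remains under either denominator.

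**The case against.** The best counter-argument is that the Protocol phrase was never meant as a missing-data rule. No passage says that a missing reading is treated as out of range. The Protocol describes the primary denominator both as interval time and as valid time, so its interval wording settles little. The SAP builds its CGM measures from data points, and a programmer working from it might well use valid time here too.

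Part of this stands: the understatement follows from the literal formula and is not a stated intention. But reading the denominator as observed time is strained, because the Protocol's next sentence defines the period as 4 hours. The SAP also extends the primary endpoint's calculation to the other percent-time endpoints and not to this one.

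The objection on size also stands. The 48% figure is relative and needs one maximal gap lying wholly inside the window on one day. The 2-hour rule does limit any single gap there. Typical capture may be high, and the loss of power in the examples above is small.

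Two stronger readings are tempting, and the documents support neither. A reader might infer that the treatment comparison is biased, but nothing shows that capture differs between arms. A reader might also infer that the primary endpoint is understated in the same way, so that the assumed 53% would become 53 × 0.85 = 45.1% at 85% capture. The synopsis and the SAP divide by valid time there, so that is not the planned analysis.

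**Conclusion.** The point holds as a specification fault in one confirmatory secondary endpoint. Its only formula, followed literally, understates the percentage whenever readings are missing, and it conflicts with the valid-time convention used for the primary endpoint. No coverage rule applies to the window.

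The worst case for one gap is 48% on one day. Under the SAP's averaging this becomes about 12% to 7% of the patient's value, if the other 3 to 6 days are complete and similar. The typical size cannot be taken from the documents; 5% applies only if capture averages 95%. The main result is lower reported arm means and a smaller absolute difference, with a little added noise from variable capture. Neither bias between arms nor a material loss of power is shown. The change should be made because it is simple and removes an ambiguity from a tested endpoint.

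**What to change.** In SAP 2.1.3.2 and 2.4.4.2, define the endpoint as in-range readings divided by valid readings in the 4 hours before injection. State that this replaces the wording in Protocol 11.4.2.2. The same sentence can confirm that daily values are averaged under SAP 2.1.3 item 9, since the Protocol formula uses only the final usable day.

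Optionally, require a minimum of valid readings in the window. Applying the existing 85% gives 0.85 × 48 = 40.8, so 41 of 48. This is a design choice; if it is adopted, the SAP should also say how many qualifying windows a patient needs.

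The cost is SAP wording and a minor programming change. The optional minimum would drop some patient-days from this endpoint; how many cannot be estimated from the documents.

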11.4.2.3 Multiplicity considerations

Results of the secondary analyses are considered as informative only if the primary analysis is positive, and will be examined in a hierarchical step-down manner. Therefore the study overall type I error does not need to be adjusted for multiplicity.

11.4.3 Analyses of safety data

All safety and tolerance results will be presented by treatment group and on the safety population using the following common rule that the baseline value will be defined generally as the last available value prior to the first injection of IMP.

For all safety data, the observation period will be divided into three segments:

- The pre-treatment phase is defined as the time between when the patients give informed consent and time of the first IMP administration (excluded).
- The on-treatment phase is defined as the time from the first IMP administration (included) until 1 day after the last dose of IMP (until midnight of day after last IMP dosing day).

The post-treatment phase is defined as the time after the on-treatment phase until the end of treatment.

Adverse events

The primary focus of AE reporting is on TEAEs. Pre- and post-treatment AEs are described separately. If an AE date/time of onset (occurrence, worsening, or becoming serious) is incomplete, an imputation algorithm is used to classify the AE as pre-treatment, TEAE, or post-treatment. The algorithm for imputing date / time of onset is conservative and classifies an AE as

a treatment emergent unless there is definitive information to determine it is pre- or post-treatment.

The following TEAEs will be summarized: Overall TEAEs, serious TEAEs, TEAEs leading to death, TEAEs leading to permanent treatment discontinuation. TEAEs will also be summarized by relationship to study treatment, and by severity. All treatment emergent SAEs will also be presented separately.

Adverse event incidence tables will present the number and percentage of patients experiencing an AE by SOC, high level group term (HLGT), high level term HLT and preferred term (PT) sorted by internationally agreed order for SOC and in alphabetical order of HLGT, HLT and PT within a SOC for each treatment group. Multiple occurrences of the same event in the same patient is counted only once in the tables within a treatment phase. The denominator for computation of percentages is the safety population within each treatment group.

Injection site reactions and hypersensitivity reactions

The number and percentage of patients experiencing injection site reactions and hypersensitivity reactions will be summarized separately.

Death

The following deaths summaries will be generated:

- Number (%) of patients who died by study period (TEAE, on-study, poststudy) and reasons for death (if available), summarized on the safety population by treatment received.
- Deaths in nonrandomized patients or randomized and not treated patients.

All TEAEs leading to death will be summarized by primary SOC, HLGT, HLT and PT, showing the number (%) of patients sorted by SOC internationally agreed order. The other levels (HLGT, HLT, PT) will be presented in alphabetic order.

Vital signs

Summary statistics for absolute values and changes from baseline of all vital signs variables, including body weight, will be calculated from the absolute values and changes from baseline for each visit or study assessment (baseline, each post baseline time point, last on-treatment during the on-treatment period of the study) by treatment.

The incidence of potentially clinically significant abnormalities (PCSA)s at any time during the on-treatment period will be separately summarized by treatment group whatever the baseline level.

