8.2.3 Timing of IMP administration

Toujeo or Lantus will be injected once daily subcutaneously as randomized in the morning, which is defined as the time period between wakeup and breakfast. The injection will be always at the same time in the morning. The clock time of the once daily Toujeo or Lantus injection (hh:mm) in the morning is at the discretion of the patient and/or investigator. However, once that time is set, the IMP must be given within a ± 1 hour window, which should be maintained for the duration of the study.

Treatment with the IMP will last until the end of treatment visit (Visit 19).

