10.1.5 End of Treatment (EOT) visit (Visit19, Week 16)

End of Treatment visit (Visit 19) will occur 7 days after Visit 18 when the patients have completed the blinded CGM. If a patient is not able to keep the visit date for any reason, he/she should inform the study site immediately to reschedule the visit as soon as possible. In such a case, the CGM system will automatically stop working and the sensor/transmitter may be removed by the patient at home or at the site later (Section 10.2.4). Before the visit day, patients should be reminded to be fasted for about 8 hours and to bring the CGM device, glucose meter, study diary, used and all unused IMP to the sites. Patient should be reminded **not to inject** the IMP and/or breakfast mealtime insulin at home if applicable since the IMP will be injected at the study site.

At this visit, quality of CGM performance will be assessed before the end of treatment. Investigators will upload the CGM data via DexCom and review the CGM summary to determine the quality of CGM performance (Section 10.2.4.2).

At this visit patients will inject the last dose of IMP which will be given after blood is drawn for laboratory measurements. In addition to all the performances done at each onsite visit, the EOT procedure will include CGM device collection, physical examination and vital signs and endpoint laboratory tests. SMPG will be uploaded, 7-point SMPG checked and all unused IMP collected.

Patients who fail to provide at least 4 days of qualified CGM data will be retrained and repeat the CGM for another week (Section 10.2.4.2). **End of treatment will be delayed accordingly**. All the procedures will be done or redone at the postponed EOT visit.

For a complete list of procedures scheduled for this study visit please refer to the Study flowchart (Section 1.2).

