10.1.6 Follow-up Visit (Visit 20)

Following the last administration of IMP (Toujeo or Lantus) either as scheduled or prematurely, a posttreatment follow-up should be scheduled for all the patients in 2 (+2) days after permanent discontinuation of the study treatment. This visit can be a phone call visit, or an on-site visit in case of ongoing or new adverse event during the posttreatment period, if needed. The patient is called by the Investigator or qualified designee at scheduled time. If the call has not been performed by the Investigator, the Investigator has to be consulted if AE/SAE and hypoglycemic event are suspected.

During the phone call the same set of questions as listed for other telephone visits has to be asked (Section 10.1.3), except IMP related questions.

IWRS/IVRS has to be called in order to register end of study.

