10.4.4 Handling of patients after permanent treatment discontinuation

Patients will be followed-up according to the study procedures as specified in this protocol up to the scheduled date of study completion, or up to recovery or stabilization of any AE to be followed-up as specified in this protocol, whichever comes last.

After permanent discontinuation of the IMP, patients will return to standard of care based on investigator and patient healthcare providers' clinical recommendation.

All cases of permanent treatment discontinuation should be recorded by the Investigator in the appropriate pages of the e-CRF when considered as confirmed.

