2.1.3.2.1 Hypoglycemia

2.1.3.2.1.1 Hypoglycemia classification

Hypoglycemia observation periods

- **Pre-treatment hypoglycemia events** are events that occur during the pre-treatment period
- **Treatment-emergent hypoglycemia events** are events that occur during the on-treatment period
- **Post-treatment hypoglycemia events** are events that occur during the post-treatment period

Hypoglycemia events will be categorized as defined in [Appendix A](#). The glucose values used to classify hypoglycemia events are from the hypoglycemia e-CRF rather than the glucose values from CGM or central laboratory.

The incidence (proportion of patients with any hypoglycemia events) and the rate (number of events per patient year of exposure) will be assessed during each safety observation period for each hypoglycemia category.

In case of some classification items are missing (i.e. assistance required or not, presence of symptom, glycemic values, use of countermeasure) to determine hypoglycemia classification (see Section 2.5.3) the following categories will be presented.

- Not classified – non severe
- Not classified – severity unknown

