2.1.4.3 Deaths

The death observation period are per the observation periods defined above.

- Death on-study: deaths occurring during the on-study observation period
- Death pre-treatment: deaths occurring before the on-study observation period
- Death on-treatment: deaths occurring during the treatment-emergent adverse event period
- Death post-study: deaths occurring after the end of the study

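### The post-treatment safety phase ends at end of treatment, before it can begin, so completers' AEs and hypoglycemia from two days after the last dose to Visit 20 have no safety phase

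*Protocol*

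**What the plan says.** Protocol 11.4.3 and SAP 2.1.4 divide all safety data into three segments: pre-treatment, on-treatment and post-treatment. The on-treatment phase runs from the first IMP administration "until 1 day after the last dose of IMP (until midnight of day after last IMP dosing day"). The third segment is then defined as follows: "The post-treatment phase is defined as the time after the on-treatment phase until the end of treatment". The sentence is the same in both documents, so neither corrects the other.

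Protocol 8.2.3 and 10.1.5 identify the end-of-treatment visit as Visit 19. Of that visit, 10.1.5 says: "At this visit patients will inject the last dose of IMP which will be given after blood is drawn for laboratory measurements".

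Safety observation continues beyond it. Under Protocol 10.1.6, "a posttreatment follow-up should be scheduled for all the patients in 2 (+2) days after permanent discontinuation of the study treatment". For patients who stop IMP early, Protocol 10.4.4 says: "Patients will be followed-up according to the study procedures as specified in this protocol up to the scheduled date of study completion". Protocol 10.5.2 likewise continues AE observation to the patient's end of study.

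Two planned outputs depend on the third segment:
- Protocol 11.4.3 and SAP 2.4.5.1 have post-treatment AEs reported separately.
- SAP 2.1.3.2.1.1 defines post-treatment hypoglycemia as "events that occur during the post-treatment period" and asks for incidence and rate in each safety observation period.

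SAP 2.1.4.3 sorts deaths by periods that it says were defined earlier. One category is "deaths occurring during the on-study observation period", but no segment in SAP 2.1.4 bears that name.

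**The concern.** A phase that starts after the last dose and closes at the end of treatment appears to close before it opens. If so, a fully dated AE found at the Visit 20 contact is too late for the on-treatment tables and cannot enter the post-treatment ones. Post-treatment hypoglycemia would have no events and no exposure time, so its rate could not be computed. The onset-imputation rule does not help, because it applies only to incomplete dates.

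The follow-up contact exists to collect safety information just after the change of basal insulin. Without a usable definition, where those events are counted would be decided at programming, after the open-label data exist.

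**Working it through.** The plan gives no figure to reproduce. The check is day arithmetic on its definitions.

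**Inputs**
- Day 1 = first IMP administration (SAP 2.5.1).
- Nominal Visit 19 = Week 16 (flow chart), so Day 1 + 16 × 7 = 113. The ±3-day window and any postponement for a repeat CGM week are ignored.
- L = day of the last IMP dose. For a completer L is the day of Visit 19 (Protocol 10.1.5).
- On-treatment ends at the close of day L + 1, so post-treatment starts on L + 2 (Protocol 11.4.3, SAP 2.1.4).
- Visit 20 falls on L + 2 to L + 4 (Protocol 10.1.6).

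**Completer** (L = 113)
- On-treatment ends: 113 + 1 = Day 114.
- Post-treatment: from Day 115 to Day 113, which is 0 days.
- Days after on-treatment up to Visit 20: (L + 2) − (L + 1) = 1, up to (L + 4) − (L + 1) = 3.

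L cancels, so the 1 to 3 days do not depend on the nominal Day 113. The patient's own end of treatment and the scheduled one coincide here, so the phase is empty on either reading.

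**Early discontinuer**, stopping at week w and followed to nominal Visit 19

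L = 1 + 7w. Days after the on-treatment phase = 113 − (L + 1).

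| Stop | L | On-treatment ends | Days from L + 2 to Day 113 |
|---|---|---|---|
| Week 2 | 15 | Day 16 | 113 − 16 = 97 |
| Week 4 | 29 | Day 30 | 113 − 30 = 83 |
| Week 8 | 57 | Day 58 | 113 − 58 = 55 |
| Week 12 | 85 | Day 86 | 113 − 86 = 27 |

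- If end of treatment means the patient's own, the phase has 0 days and every day in the last column is unclassified. SAP 2.5.4 fits this reading, since it uses the term for assessments made when a patient stops early.
- If it means the scheduled Visit 19, the same days are all post-treatment and are covered to that date. The protocol's title for Visit 19 supports this reading.

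**Comparison with the plan's other windows**
- SAP 2.1.2 runs post-treatment medications from the last injection + 2 days to the end of the study. The general start is the same as for the safety phase; the closing point is different.
- Protocol 10.5.2 also uses the patient's end of study for AE observation.

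With that closing point, a completer's phase runs from Day 115 to Day 115–117 (1 to 3 days) and includes Visit 20. An early discontinuer's phase runs from L + 2 to the end of that patient's study.

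**The case against.** The strongest reply is that the intent is obvious and nothing is lost. AEs are recorded to the end of the study, post-treatment AEs are to be described separately, and the parallel medication window already closes at the end of the study. TEAEs are the main focus, and no confirmatory test uses this phase. All of that stands. It limits the consequence to classification but does not supply a working rule, because both documents state the same one.

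Four stronger readings are tempting, and the documents do not support them.

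- A reader might infer that deaths drop out of the tables. The planned death summaries use treatment-emergent or on-treatment, on-study and post-study (Protocol 11.4.3, SAP 2.4.5.2), not the post-treatment phase.
- A reader might infer that the on-study period has no basis in the SAP. SAP 2.1.4.1, like Protocol 9.3.2.1, gives a study observation period from randomization to the end of the study. The label differs and should be tied to it. Starting on-study at the first IMP dose would conflict with that text, because Protocol 8.2.4 allows the first dose the next morning.
- A reader might infer that hypoglycemia after an early stop goes unanalysed. SAP 2.1.3 also analyses efficacy parameters, hypoglycemia included, over a randomized period from first dose to Visit 19. What is missing is the safety-phase label, plus the days after Visit 19.
- A reader might infer that a Week 1 stop always loses about 15 weeks (L = 8; 113 − 9 = 104 days; 104 / 7 = 14.9 weeks). That needs the patient's-own reading and follow-up to Week 16. Protocol 10.4.4 and 10.5.2 provide for such follow-up, but 10.1.6 places Visit 20 shortly after a premature stop too and registers end of study there.

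Nor are all 616 planned patients affected. The phases are anchored to IMP doses, so only treated patients have them, and only those with an event in the gap are misplaced.

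**Conclusion.** The point holds as a defect in an operative definition. For completers the post-treatment phase has 0 days whichever way end of treatment is read, and AEs and hypoglycemia over the 1 to 3 days from L + 2 to Visit 20 belong to no safety phase. Events up to the close of day L + 1 remain on-treatment and are unaffected.

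For early discontinuers the size is conditional: 27 to 97 days to nominal Visit 19 for stops at Week 12 to Week 2 on the patient's-own reading, and none to that date on the scheduled-visit reading. Both figures assume follow-up continues to Visit 19. The documents do not say how many patients are expected to stop IMP and stay under observation; the roughly 15% drop-out in SAP 1.3 is an allowance for evaluability, not that number.

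Data collection, efficacy tests and the planned death tables are not affected. It should still be corrected before database lock, because a planned safety output cannot be produced as defined for completers.

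**What to change.** - In Protocol 11.4.3 and SAP 2.1.4, close the post-treatment phase at *the end of the study (Visit 20 or last study contact)* instead of the end of treatment. This agrees with Protocol 10.5.2 and SAP 2.1.2.
- In SAP 2.1.4.3, tie on-study to the study observation period in SAP 2.1.4.1 (randomization to end of study) rather than create a new definition from the first IMP dose. Add that on-treatment deaths are a subset of on-study deaths, so the death categories are nested, not exclusive.
- Reconcile Protocol 10.4.4 and 10.5.2 with 6.2.1 and 10.1.6 on when the study ends for a patient who stops IMP early, since that date will close the phase.

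The cost is one phrase in each document, one cross-reference with a note, and one point of reconciliation. Programming impact is negligible, and sample size, type I error and the efficacy models do not change.
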